7.0 STUDY PROCEDURES

Figure 7.1 contains a flowchart of the study procedures. This research protocol does not require withholding or postponing any medically indicated customary health care. Subjects will be carefully monitored during the course of the trial. If complications occur, the investigator will use good clinical judgment and administer all necessary clinical care.

Note:

Patients are considered enrolled in the study when informed consent is signed, all screening criteria have been met, and the first RheOx treatment activation is administered.

Figure 7.1: Study Procedures

7.1 Treatment Plan

Following screening and enrollment, subjects will undergo two bronchoscopic procedures (Visit 2 and Visit 4) both of which include treatment with the investigational device. Bronchoalveolar Lavage (BAL) will also be completed during the bronchoscopy prior to the initiation of RheOx treatment.

Investigational treatment with RheOx will be administered to the right lung during bronchoscopy #1 (Visit 2) and to the left lung during bronchoscopy #2 (Visit 4). Each activation will deliver 5 packets of electrical pulses synchronized with the cardiac cycle such that 1 packet is delivered with each cardiac cycle.

The IVY cardiac monitor will be utilized to monitor cardiac activity during the RheOx Bronchial Rheoplasty in this study. The IVY will be set with heart rate alarm limits of less than 30 beats per minute (BPM) and greater than 130 BPM. Anesthesiologists assigned to the study will be trained on IVY alarm signal and its indication. Anesthesiologists will be instructed to use their best clinical judgement and follow standard of care procedure should the IVY monitor alarm during the bronchoscopy procedure.

The total number of activations is at the discretion of the treating physician in order to completely treat accessible airways in the designated treatment areas. The number of activations is dependent upon patient anatomy including airway diameter, airway length and airway accessibility and typically range between 30 and 60 activations per lung. In some cases, bronchoscopists may be able to access more distal subsegmental airways, delivering additional activations occasionally totaling over 100 activations.

Note:

A therapeutic bronchoscope having at least a 3.0 mm working channel, such as the Olympus model 1T180, is required for use with the RheOx Catheter.

Specimen/fluid from the BAL is used to assess pathogens and cell composition in the airways as well as markers for inflammation. Samples will be collected at each bronchoscopy and compared to determine whether any changes occur after the use of RheOx. BAL instructions are included in the study operational instruction manual.

7.2 Description of Visits

7.2.1 Visit #1. Screening and Enrollment

Subjects who meet the eligibility criteria and have signed an informed consent form may be enrolled in the study. Assessments performed exclusively to determine eligibility for this study will be done only after obtaining signed informed consent from the subject. Assessment performed for clinical indications (i.e., not exclusively to determine study eligibility) may be used for screening evaluation even if the studies were completed before informed consent was obtained.

All screening procedures must be completed within 90 days prior to start of study treatment.

Note: If the subject experiences a COPD exacerbation or other change in functional status between screening and the first bronchoscopy, screening procedures should be repeated as appropriate at the investigator's discretion. Refer to the Table 7.1 Schedule of Events for listing of required screening procedures.

General Screening Notes:

High Resolution CT Scan

High resolution computed tomography (HRCT) is incorporated as a tool to define subject inclusion criteria and to assess post treatment changes. CT acquisition will be per the CT Core Manual provided separately to each site upon completion of training by the designated CT core lab for this study.

7.2.2 Visit #2. Bronchoscopy #1 / Treatment Session #1

Eligible subjects are scheduled for the first bronchoscopy and treatment session within 90 days of completing screening procedures. Pre-operative procedures (e.g., physical exam, complete blood count) are completed in accordance with the Schedule of Events table prior to the bronchoscopy.

Note: Pre and post-bronchoscopy care (including medications) should be administered at the discretion of the treating physician per the institution's standard of care.

Upon successful completion of the preoperative procedures, the subject undergoes a bronchoscopy procedure in accordance with standard institutional protocol. Anesthesia is administered. The airways are visualized, and BAL completed. If any complications that preclude continued participation in the study are revealed, then the treatment is halted. If subject has not experienced any complications that precludes continued participation in the study, then RheOx therapy is administered to the target sites in the right lung in accordance with the instructions for use. The clinical investigator ensures FiO₂ does not exceed 40% during energy delivery. Prior to the initiation of energy delivery and during at least one energy delivery a 6 second 3 lead EKG strip is recorded. An EKG rhythm strip from anesthesia monitoring is adequate.

The subject is recovered in accordance with standard institutional procedures. The study investigator determines whether an overnight stay is clinically warranted, and the subject is discharged at the investigator's discretion. Any observed adverse events are reported accordingly.

Note: Subjects may be excluded or treatment delayed at the investigator's discretion if the patient has an active respiratory infection (e.g., common cold, pneumonia, MAI), COPD exacerbation or any other significant adverse event that may compromise the procedure.

Likewise, if at the time of the scheduled procedure the study physician determines the patient has clinical signs or findings (i.e., pulmonary nodule requiring follow-up, abnormal cardiac rhythm) that may adversely impact the

safety of the procedure, the procedure will be postponed pending treatment of the condition and reassessment of the patient.

7.2.3 Visit #3. 1-week Follow-up Visit

Subjects are scheduled for follow-up one week (7 days \pm 3 days) following Bronchoscopy #1. The visit will include a physical exam and assessment of AEs and medications in accordance with the Schedule of Events table.

7.2.4 Visit #4. Bronchoscopy #2 / Treatment Session #2

Subjects are scheduled for follow-up 3-6 weeks following Bronchoscopy #1. Pre-operative procedures (e.g. CT Scan, physical exam, CBC) are completed in accordance with the Schedule of Events table prior to the bronchoscopy. Any observed adverse events are reported accordingly. If the subject has experienced any complications that preclude continued participation in the study, then additional treatment is halted.

Upon successful completion of the pre-operative procedures, the subject undergoes a bronchoscopy procedure in accordance with standard institutional protocol. Anesthesia is administered. The airways are visualized, and BAL completed. The RheOx Bronchial Rheoplasty is administered to the target sites in the left side lung in accordance with the instructions for use. The clinical investigator ensures FiO₂ does not exceed 40% during energy delivery. Prior to the initiation of energy delivery and during at least one energy delivery a 6 second 3 lead EKG strip is recorded. An EKG rhythm strip from anesthesia monitoring is adequate.

The subject is recovered in accordance with standard institutional procedures and observed overnight at the discretion of the study investigator. The subject is then discharged at the investigator's discretion. Any observed adverse events are reported accordingly.

Note: Bronchoscopy #2 may be delayed or halted at the investigator's discretion if the patient has an active respiratory infection (e.g., common cold, pneumonia, MAI), COPD exacerbation since treatment session #1 or any other significant clinical symptom that may compromise the procedure.

7.2.5 Visit #5. 1-week Follow-up

Subjects are scheduled for follow-up one week (7 days \pm 3 days) following Bronchoscopy #2. The visit will include a physical exam and assessment of AEs and medications.

7.2.6 Visit #6. 1-month Follow-up

Subjects are scheduled for follow-up one month (1 month \pm 7 days) following Bronchoscopy #2. The visit will include a physical exam and assessment of AEs and medications.

7.2.7 Visits #7 In-office Follow-up Visit (3 months post Bronchoscopy # 2)

Subjects will return for follow-up visits at 3 months \pm 2 weeks after Bronchoscopy #2 (Visit 4). Refer to the Schedule of Events table for a complete listing of required tests.

7.2.8 Visits #8 In-office Follow-up Visit (6 months post Bronchoscopy # 2)

Subjects will return for follow-up visits at 6 months \pm 4 weeks after Bronchoscopy #2 (Visit 4). A CT Scan will be performed as part of this visit. Refer to the Schedule of Events table for a complete listing of required tests.

7.2.9 Visit # 9 Phone Call Visit (10 months post Bronchoscopy # 2)

The study coordinator / research nurse calls the subject on the telephone 10 months \pm 2 weeks. Any adverse events or changes in medication are reported accordingly. A study visit may be scheduled if clinically warranted.

7.2.10 Visits # 10, 11, 12, 13 and 14 In-office Follow-up Visits (Annual Follow-up post Bronchoscopy # 2)

Subjects will return for follow-up visits at 12 months \pm 4 weeks after Bronchoscopy #2 (Visit 4) and annually thereafter for 5 years (\pm 4 weeks). Refer to the Schedule of Events table for a complete listing of required tests.

Note: If the subject experiences a COPD exacerbation or other change in functional status within 6 weeks of any scheduled follow-up visit, the investigator should consider rescheduling study follow-up visits based on his or her best medical judgement to allow for a true assessment of the patient's stable condition once the subjects symptoms have returned to normal. It is recommended that subjects return to clinical baseline for a minimum of two-weeks prior to undergoing study specific follow-up testing.

7.3 Concomitant Medications / Treatments

Subjects should be treated for COPD before enrollment according to the appropriate ATS guidelines at the discretion of the study investigator and will remain on current (pre-investigational treatment) bronchitis/COPD medications (e.g., long-acting bronchodilators (LABA), long-acting muscarinic antagonists (LAMA), inhaled corticosteroids (ICS)) through the 1-year evaluation unless adjustment is deemed appropriate or medically necessary by the study investigator. Effort should be made to hold dosing constant.

Subjects who are treated with more than 10 mg oral corticosteroids (prednisolone/ prednisone) daily are excluded. Patients treated with oral corticosteroids (prednisolone/ prednisone) \leq 10mg per day may be enrolled in the study. Pre-procedural, peri-procedural or post-treatment corticosteroids (IV or oral) may be administered if medically necessary at the discretion of the study investigator.

If applicable, it is recommended subjects temporarily stop taking anticoagulants (e.g., warfarin, Xarelto) prior to each bronchoscopy, as directed by the study investigator. Aspirin may be taken at the discretion of the study investigator.

Perioperative antibiotics are not recommended unless deemed medically necessary by the study investigator. If necessary, a non-macrolide antibiotic (e.g., Cipro, Augmentin) is preferred.

7.4 Schedule of Events (Table 7.1)

Table 7.1: Schedule of Events

	Visit #1: Screening	Visit #2: Bronchoscopy #1	Visit #3: Follow-up 1 week Post-Bronchoscopy #1	Visit #4: Bronchoscopy #2	Visit #5: Follow-up 1 week Post-Bronchoscopy #2	Visit #6: Follow-up 1 month Post-Bronchoscopy #2	Visit #7: Follow-up 3 month Post-Bronchoscopy #2	Visit #8: Follow-up 6 month Post-Bronchoscopy #2	Visit #9: Follow-up Phone Call 10 month Post-Bronchoscopy #2	Visit #10-14: Annual Follow-up 1 - 5 years Post-Bronchoscopy #2
Window			± 3 days	-3 to +6 weeks	± 3 days	± 7 days	± 2 weeks	± 4 weeks	± 2 weeks	± 4 weeks
Informed Consent	X									
Inclusion/Exclusion Criteria	X									
Medical History	X									
Exacerbations History	X	X	X	X	X	X	X	X	X	X
Concomitant Meds	X	X	X	X	X	X	X	X	X	X
Adverse Events		X	X	X	X	X	X	X	X	X
Physical Exam	X	X ¹	X	X ¹	X	X	X	X		X
CBC & Blood Panel	X	X ¹		X ¹			X	X		X
Cotinine Test	X									
EKG	X	X ⁴		X ⁴			X	X		X
Spirometry	X			X ¹			X	X		X
DLCO/Body Pleth	X			X ¹			X	X		X
Six Minute Walk Test	X									
CT Scan	X			X ¹				X		
Bronchoscopy		X		X						
Bronchoalveolar lavage		X		X						
RheOx Bronchial Rheoplasty		X		X						
Induced Sputum Sample	X						X	X		X
SGRQ	X			X ¹			X	X		X
CAT Score	X			X ¹			X	X		X
CASA-Q	X			X ¹			X	X		X
ISI ⁵	X			X ¹			X	X		X
Cough Counting Monitor ⁶	X						X	X		X ⁷
EXACT-PRO ⁸	X	DAILY								
Note 1:	Noted activities are completed prior to bronchoscopy.									
Note 2:	Adverse Events are noted before and after bronchoscopy.									
Note 3:	Overnight Hospital Stay at discretion of PI									
Note 4:	An EKG is recorded prior to the initiation of RheOx procedure and during at least one energy delivery; anesthesia EKG may be used.									
Note 5:	Subjects with clinically significant insomnia at baseline as defined by a ISI score of ≥ 8 points ²¹ , may be asked to complete optional polysomnography testing at baseline and 3-months follow-up.									
Note 6:	In this study, VitaloJAK cough monitor is an exploratory outcome measure. Patients willing to participate are encouraged to wear the 24 hour cough monitor at the 4 visits specified, but it is not mandatory.									
Note 7:	12-month visit only									
Note 8:	In this study, EXACT-PRO is an exploratory outcome measure to quantify and measure exacerbations of COPD. Patients are encouraged to complete the questionnaire daily during the first year (up to Visit #10), but it is not mandatory. Daily patient compliance will not be a reason for removal from the study.									

Additional Notes on Schedule of Events:

Note: If Bronchoscopy #2 cannot be completed the subject should continue follow-up at 3 months, 6 months, 12 months and annually through 5 years following Bronchoscopy #1 (i.e., last treatment session).

Note: If the subject experiences a COPD exacerbation or other change in functional status within 6 weeks of any scheduled follow-up visit, the investigator should consider rescheduling study follow-up visits based on his or her best medical judgement to allow for an accurate assessment of the patient's stable condition once the subjects symptoms have returned to normal. It is recommended that subjects return to clinical baseline for a minimum of two-weeks prior to undergoing study specific follow-up testing.

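### Subjects who do not complete the second treatment are listed for fewer adverse event and exacerbation contacts, leaving about six months without scheduled contact before the 12-month visit

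*Protocol*

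**What the plan says.** Protocol Table 7.1 schedules adverse events, exacerbation history and concomitant medications at every post-treatment contact. After the second treatment these contacts fall at 1 week and at 1, 3, 6, 10 and 12 months, then annually. All are anchored to Bronchoscopy #2. For the 1-month visit, Section 7.2.6 says "Subjects are scheduled for follow-up one month" after that procedure. For the 10-month contact, Section 7.2.9 says "The study coordinator / research nurse calls the subject on the telephone 10 months", under a heading that counts from Bronchoscopy #2.

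One note, among the additional notes to Section 7.4, covers subjects without a completed second procedure: "If Bronchoscopy #2 cannot be completed the subject should continue follow-up at 3 months, 6 months, 12 months and annually through 5 years". It counts from Bronchoscopy #1 as the last treatment session. No other passage gives these subjects a follow-up schedule.

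Two earlier contacts do not depend on the second treatment. Section 7.2.3 sets a visit after Bronchoscopy #1 ("Subjects are scheduled for follow-up one week"), and Section 7.2.4 sets Visit 4 ("Subjects are scheduled for follow-up 3-6 weeks following Bronchoscopy #1").

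Section 7.2.4 also gives reasons for not treating the second lung: "If the subject has experienced any complications that preclude continued participation in the study, then additional treatment is halted", and "Bronchoscopy #2 may be delayed or halted at the investigator's discretion if the patient has an active respiratory infection", with exacerbation and other significant symptoms listed as well. Section 7.5 adds voluntary withdrawal from treatment with follow-up allowed.

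The SAP analyses everyone who had at least one treatment as a single population (Section 4.2.1). It reports exacerbations by severity per patient-year (Section 4.8.2.1), sets them beside the prior-year rate (Table 14.3.8), and makes no evaluation of missing data (Section 5.2).

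**The concern.** How often a subject is asked about adverse events and exacerbations depends on whether the second treatment was completed, and completion depends partly on how the subject fared after the first. Fewer scheduled contacts therefore fall on a group partly selected by clinical problems.

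The events at risk are those that reach the database mainly because someone asks. By the protocol's definitions, mild and moderate exacerbations are treated with short-acting bronchodilators, antibiotics or oral corticosteroids, without hospital or emergency care. Non-serious adverse events are similar. Over a longer recall interval such events may be forgotten or misdated, while the subject still contributes full person-time to the pooled rate. Any loss would lower the post-treatment exacerbation rate relative to the prior-year rate shown beside it.

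The daily EXACT-PRO diary does not fill the gap. It is optional in the first year (Table 7.1, Note 8), and SAP Section 4.9.4.5 says it will not be summarised.

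**Working it through.** The plan states no figure to reproduce, so the check counts contacts and gaps.

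**Inputs.** Contact times come from Table 7.1, Sections 7.2.3 to 7.2.10 and the note. They are placed at nominal days after the last treatment: 1 week = 7, 1 month = 30, 3 months = 91, 6 months = 182, 10 months = 304, 12 months = 365. Visit 4, at 3 to 6 weeks after Bronchoscopy #1, falls on day 21 to 42.

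**Year after the last treatment.**

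| Subject | Contact days | Contacts | Gap before the 3-month visit | Longest gap |
|---|---|---|---|---|
| Two lungs treated | 7, 30, 91, 182, 304, 365 | 6 | 91 − 30 = 61 | 304 − 182 = 122 |
| One lung, note as written, no Visit 4 | 7, 91, 182, 365 | 4 | 91 − 7 = 84 | 365 − 182 = 183 |
| One lung, Visit 4 attended | 7, 21 to 42, 91, 182, 365 | 5 | 49 to 70 | 365 − 182 = 183 |

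The shortfall is (6 − 4)/6 = 33%, or (6 − 5)/6 = 17% when Visit 4 takes place. Placing the 3-month visit at day 90 makes the early gap 83 days.

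**Window edges.** The 6- and 12-month visits each allow ±4 weeks, so the late gap can reach 183 + 28 + 28 = 239 days. For two-lung subjects, the gap from the 6-month visit to the 10-month call (±2 weeks) can reach 122 + 28 + 14 = 164 days.

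**From the index procedure to the 12-month visit.** Two-lung subjects have 9 contacts (Visits 2 to 10) over 21 + 365 = 386 to 42 + 365 = 407 days. One-lung subjects have 5 (Visits 2, 3, 7, 8 and 10), or 6 with Visit 4, over 365 days.

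**Number affected.** The protocol gives no expected number. Its only related figure is the first-in-human count in Section 1.3: 25 right-lung and 22 left-lung procedures. If all three of the difference were permanent non-completers (assumption), the proportion is 3/25 = 12%, exact 95% interval 2.5% to 31%. Applied to 30 subjects, that is 3.6, range about 1 to 9. The count is a data cut in a study still treating patients, so the three may have been waiting for the second procedure. It is an illustration, not a bound, and the true number could be lower.

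**The case against.** **The note cancels nothing.** It says when follow-up should continue, and 3, 6 and 12 months are the visits with questionnaires, spirometry and laboratory tests, so it could be read as re-anchoring the testing visits only. The synopsis also lists visits in abbreviated form for everyone. An unintended omission is possible. Even so, the synopsis leaves out the 3-month visit and the note does not, so the note looks like a working list, and no other text gives these subjects the two contacts. Sites can be expected to follow it.

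**Visit 4 covers most of the early gap.** This stands. Section 7.2.4 places the decision to halt treatment around that visit, and adverse events, exacerbations and medications are collected there. The remaining 49 to 70 days to the 3-month visit is close to the two-lung figure of 61. The early gap is fully open only for subjects stopped beforehand. Visit 4 does nothing for the gap between 6 and 12 months.

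**The primary outcome hardly depends on these contacts.** This largely stands. Death, hospital stays and ventilation beyond 24 hours are likely to become known anyway. The pneumothorax and pneumonia windows (2 and 7 days) lie around the retained 1-week visit. Adverse events are assessed to the end of the study, and later visits cover earlier intervals, so a missing call postpones collection and does not remove it. What remains exposed is recall of milder events.

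**Stronger readings that the documents do not support.** A reader might infer that serious event reporting slows. Section 10.1.2 runs that reporting from when the investigator learns of the event, independently of visits, and nothing shows a delay. A reader might also infer that the SAP's recovery period lacks a closing contact in these subjects. SAP Section 4.8.2 ends that period 30 days after the second procedure, so it defines no such period for someone who never had one. That missing anchor is a separate matter. Nor do the documents show that one-lung subjects are the most likely to have been harmed, since voluntary withdrawal is another route.

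**Conclusion.** The point holds as a gap in follow-up scheduling with a possible, unquantified effect on milder safety data. Read as written, the note gives one-lung subjects 4 scheduled contacts in the year after the last treatment, or 5 with Visit 4, against 6. Its firm consequence is the loss of the 10-month call, which leaves about 183 days rather than about 122 without scheduled contact inside the 12-month safety window. The loss of the 1-month contact is material mainly for subjects stopped before Visit 4.

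The conclusion assumes that sites apply the note literally and that some subjects do not complete the second procedure. Lower or less well-dated ascertainment of non-serious adverse events and mild or moderate exacerbations is plausible. The documents do not demonstrate that it will occur, and they fix neither the size of the group nor the size of any bias. With up to 30 subjects, a few people can still move a pooled per-patient-year rate, and safety is the primary objective, so the note is worth correcting.

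**What to change.** Amend the note in Section 7.4 so that a subject who does not complete Bronchoscopy #2 keeps, timed from Bronchoscopy #1 and in addition to the 3-, 6- and 12-month and annual visits:

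- a 1-month contact for adverse events, exacerbations and medications, by telephone or met by an attended Visit 4;
- the 10-month telephone call.

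Without Visit 4, contacts rise from 4 to 6 and the longest gap falls from about 183 to about 122 days, matching two-lung subjects. With Visit 4 serving as the 1-month contact, adding the call brings the count from 5 to 6.

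The cost is one amended sentence and up to two short contacts per affected subject. The change concerns data collection only and leaves treatment decisions as they are.
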